4.2 Secondary

1) Quantify the frequency of proper treatment changes directed by PSMA-PET

2) Compare PSMA-PET performance for predicting extra-prostatic extension to standard-of-care assessments.

Exploratory Endpoints:

3) Assess quality of life changes from preoperative baseline:

IEF-15 (Erectile function score),

EPIC-26 (Pad use),

SF-36 (Overall mental and physical health domains)

4) To assess whether kinetic modeling tools are useful for improving detection of the location and extent of tumor in ^{68}Ga -PSMA-11 PET/CT images. (Going beyond the standard PET map of regional radiotracer concentrations, to additionally examine differences in regional pharmacokinetics in order to possibly better differentiate benign and neoplastic tissue.)

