5.2 Secondary

1) Rate of treatment changes and rate of treatment changes that were appropriate based on pathology.

Exploratory Endpoints

- 2) Sensitivity/ Specificity/ PPV/ NPV for PSMA-PET vs. MRI vs. ultrasound-based nomogram.
- 3) IIEF-15 (Erectile function score), EPIC-26 (Pad use), SF-36 (overall mental and physical health domains).
- 4) Qualitative and quantitative evaluation of changes in PET image appearance after voxel-by-voxel application of kinetic modeling tools to define regional pharmacokinetics (compared to standard PET reconstructions showing simply the integrated concentration of regional radioactivity over the imaging period).

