10.6 Analysis of Secondary Objectives

The frequency of proper treatment changes directed by PSMA-PET compared to MRI will be summarized along 95% CI for all evaluable subjects, and separated for 3 areas important for genito-urinary function including: 1) Bladder neck, 2) Nerve bundles, 3) Urethral Sphincter (Figure 4). We will use the McNemar test to compare the sensitivity and specificity values between PET and MRI although data from this pilot study is considered hypothesis generating only due to the small sample size.

The quality of life data including IIEF-15 (Erectile function score), EPIC-26 (Pad use), SF-36 (overall mental and physical health domains) are longitudinal data, which will be analyzed separately. The analysis will start with the graphical representation of the data, where

mean and the standard of mean at each time point will be plotted and linked over time. An exploratory statistical modelling approach will be conducted to analyze the change over time. In particular, a mixed effects model will be used to analyze the data.

The parametric kinetic modeling data will be assessed for goodness-of-fit of the measured regional tissue time-activity curves to the applied kinetic model. Additionally, the images derived by voxel-wise kinetic modeling will be visually compared to standard reconstructions of the integrated regional concentration of radioactivity, assessing apparent lesion size, lesion position, and lesion/background contrast.

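### The kinetic-image comparison in 10.6 lists lesion/background contrast but no voxel-noise or precision measure, so higher contrast alone could be read as better detection

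*Combined protocol and SAP*

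**What the plan says.** Section 4.2, item 4, states the aim: "To assess whether kinetic modeling tools are useful for improving detection of the location and extent of tumor". Section 5.2 places the matching endpoint under "Exploratory Endpoints" and words it as "Qualitative and quantitative evaluation of changes in PET image appearance after voxel-by-voxel application of kinetic modeling tools". The product is thus a voxel-level image, and part of its evaluation is meant to be quantitative.

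Section 10.6 gives two assessments. First, the kinetic data are "assessed for goodness-of-fit of the measured regional tissue time-activity curves to the applied kinetic model". Second, "the images derived by voxel-wise kinetic modeling will be visually compared to standard reconstructions", "assessing apparent lesion size, lesion position, and lesion/background contrast".

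Neither 10.6 nor any other section mentions image noise, contrast-to-noise, precision of the fitted voxel parameter, or false lesions in this comparison. No kinetic model is named, and there is no score or threshold for calling one image better. Section 8.3.2 plans to fuse the PET with lesion maps from whole-mount pathology, but 10.6 does not use those maps here.

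**The concern.** The two assessments do not reach the property that the objective needs.

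- **Fit is regional; the image is voxel-wise.** A regional curve averages many voxels. It can fit well while the individual voxel estimates are unstable.
- **Contrast is not detectability.** A lesion stands out when its difference from background is large relative to the variation in that background. A lesion/background ratio has no term for that variation.

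The ratio also tends to move one way. An uptake-rate image removes the blood and free-tracer part of the signal, which is normally a larger share of background than of lesion. The rate is a fitted slope, which usually carries more voxel noise than activity averaged over a late window. The feature that speaks most directly to conspicuity may therefore favour the kinetic image almost automatically, while the cost in noise goes unrecorded. At stake is how exploratory objective 4 is interpreted.

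**Working it through.** The plan gives no figure for this comparison, so there is nothing of its own to reproduce. Steps 2 to 4 are illustrations, and their kinetic and noise inputs are assumptions.

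**1. Why the ratio rises under a Patlak-type model.** Let K be the uptake rate, V the distribution volume, Cp plasma activity and Θ = ∫Cp / Cp. Late tissue activity divided by Cp is KΘ + V.

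- Static ratio = (K_L Θ + V_L) / (K_B Θ + V_B)
- Kinetic ratio = K_L / K_B

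Cross-multiplying, the kinetic ratio is larger exactly when K_L V_B > K_B V_L. With V_L = V_B this reduces to K_L > K_B, which holds for any lesion with the higher rate. Noise does not enter. If the lesion's distribution volume is larger than benign tissue's in at least the same proportion as its rate, the result fails.

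**2. Break-even noise at the protocol's own uptakes.** Section 3.1 reports a median index-lesion SUV of 10.0 and a median benign SUVmax of 2.2, so R = 10.0/2.2 = 4.55. Define CNR = (lesion mean − benign mean) / voxel SD in benign tissue. Hold the background mean fixed and multiply contrast by c. CNR then falls below that of the standard image once background noise rises by more than (cR − 1)/(R − 1).

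| Assumed contrast gain | New ratio cR | Break-even noise multiple |
|---|---|---|
| 25% | 5.68 | 4.68/3.55 = 1.32 |
| 50% | 6.82 | 5.82/3.55 = 1.64 |
| 100% | 9.09 | 8.09/3.55 = 2.28 |

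With contrast up 50% and noise tripled, CNR is 1.64/3 = 0.55 of the standard image, yet the contrast feature still favours the kinetic image.

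**3. Simulated kinetics, homogeneous background.** Assumptions: rate image fitted by weighted slope to the 10–15, 20–30 and 40–55 minute windows or to 1-minute frames; 40–55 minute static comparator; 15% background voxel CV from counts; lesion rate 0.03–0.10/min; background rate 0.005–0.01/min; V 0.2–0.8; three plasma tails.

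- In all 72 scenarios the ratio rose (10% to 141%, median 39%) and CNR fell (18% to 46%, median 35%).
- One unweighted example (lesion 0.05, background 0.005, V 0.4) gave a ratio of 6.1 static and 10.0 kinetic, with CNR 34.2 and 21.3. The implied kinetic background CV is (10.0 − 1)/21.3 = 42%, about 2.8 times the static 15%. Break-even was (10.0 − 1)/(6.1 − 1) = 1.76 times.
- Extending the fit to 10–60 minutes, in a separate analytic version with other plasma tails, CNR fell in 33 of 36 cases (range −36% to +2%).

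**4. Simulated kinetics, heterogeneous background.** A similar 72-scenario grid let V vary between benign voxels. The share of scenarios in which CNR *rose* was:

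| Voxel variation in V | 15% count noise | 5% count noise |
|---|---|---|
| 20% | 3% | 74% |
| 40% | 57% | 100% |

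The ratio results barely changed. The direction of CNR therefore turns on two quantities that the documents do not state.

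**The case against.** The strongest reply has four parts.

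- **No scoring rule exists.** A reader might infer that a noisier kinetic image would be scored as the winner. The documents do not support that: the comparison is visual and no direction of better is defined. This stands. The most that can be said is that such an image could be judged better.
- **Size and position are also listed.** They correspond to location and extent in the objective, noise can distort both, and someone viewing the images sees noise directly. This is fair, but neither feature measures noise and nobody is asked to record it. Of the three features, contrast speaks most directly to conspicuity.
- **The fall in CNR depends on assumptions.** A reader might infer from step 3 that kinetic imaging lowers CNR. Step 4 shows that this comes from assuming a homogeneous background. The plan names no model, and 8.3.2 speaks of multi-parametric analysis with an early, finely framed input function, so a late-data slope is only one possibility. This stands.
- **Lower CNR is not lost detection.** In the worked example the lesion is still about 21 background SDs above benign tissue, and no detection rate was computed. Nothing here shows that tumour would be seen less reliably or that a reported benefit would be false.

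A pass/fail gate on CNR would also be hard to defend for an exploratory description. A kinetic image could delineate tumour better by removing non-specific uptake without a higher CNR. That argues for adding the measure alongside contrast, not replacing contrast with it.

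**Conclusion.** The point holds as a gap in what is measured. Section 10.6 evaluates a voxel-wise image with a regional fit check and three visual features, and none of these captures voxel noise or precision. Under a Patlak-type rate image with similar distribution volumes, higher contrast is close to automatic and is weak evidence of better detection. CNR is the more informative measure because it can go either way.

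The size in this trial cannot be determined from the documents. The break-even multiples of 1.32 to 2.28 rest on assumed contrast gains and on the medians from the earlier series, where the benign value is an SUVmax. The simulated changes rest on assumed kinetics and noise.

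The consequence is limited: this is an exploratory endpoint of a single-arm pilot, the sample size does not rest on it, and the primary sensitivity and specificity analysis is untouched. It is a cheap improvement, not a defect that threatens the trial.

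**What to change.** In 10.6, keep size, position and contrast, and add:

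1. **Contrast-to-noise ratio**, (lesion mean − benign-prostate mean) / voxel SD in benign prostate. It has no units, so rate and activity images can be compared directly. The SD includes count noise and real heterogeneity, both of which compete with the lesion.
2. **Same volumes on both images**, defined from the whole-mount lesion mapping already planned for fusion in 8.3.2.
3. **A paired summary**: the within-patient difference in CNR, kinetic minus static, with a 95% CI. State which static time window is the comparator and how several lesions in one patient are combined.
4. **Voxel-level precision**: the coefficient of variation of the fitted parameter across benign-prostate voxels, reported beside the regional fit.
5. **One sentence on interpretation**: improved detection will not be claimed from higher contrast alone.

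The cost is SAP wording and a little more analysis on images and mappings that the trial already plans to produce. No patient procedure changes. The downside is that the kinetic result may look less favourable.

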11 DATA FORMS AND SUBMISSION SCHEDULE

This study will utilize the secure, web-based, Research Electronic Data Capture (REDCap) system for data input. REDCap was developed by Vanderbilt University and is provided by Indiana University through their community license. REDCap is managed by the Indiana University Department of Biostatistics and secured by University Information Technology Services Advanced IT Core. Access to the password protected database will be limited to the investigators of this study, and any data that is distributed will be either de-identified or authorized by written permission from the subject.

All source documents are to remain in the patient's clinic file. All documents should be kept according to applicable federal guidelines.

12 DATA AND SAFETY MONITORING PLAN

This study will be conducted in accordance with the IU Simon Cancer Center Institutional DSMP for High Risk Trials.

Investigators will conduct continuous review of data and subject safety. Weekly review meetings for high risk trials are required and will include the principal investigator, clinical research specialist and/or research nurse (other members per principal investigator's discretion). Weekly meeting summaries should include review of data and subject safety by including for each dose level: the number of subjects, significant toxicities as described in the protocol, dose adjustments and responses observed. Study teams should maintain meeting minutes and attendance for submission to the DSMC upon request.

Data and Safety Monitoring Committee

The IUSCC Data and Safety Monitoring Committee (DSMC) is responsible for oversight of subject safety, regulatory compliance, and data integrity for this trial. The DSMC will

Version Date: 03/29/2022

Page: 24

review this study semi-annually to review overall trial progress, toxicity, compliance, data integrity, and accrual per the Institutional DSMP.

Furthermore, the DSMC conducts an administrative review of serious adverse events (SAEs), deviations, reportable events, and any other outstanding business. Major issues may require further DSMC review or action.

For any increase in frequency of grade 3 or above adverse events (above the rate reported in the Investigator Brochure or package insert), the principal investigator will notify the DSMC Chair immediately. The notification will include the incidence of study adverse events, grades, and attributions, as well as investigator statements regarding comparison with risks per the IB/ package insert.

At any time during the conduct of the trial, if it is the opinion of the investigators that the risks (or benefits) to the subject warrant early closure of the study, the DSMC Chair and Compliance Officer must be notified within 1 business day via email, and the IRB must be notified within 5 business days. Alternatively, the DSMC may initiate suspension or early closure of the study based on its review.

12.1 IND Annual Reports

For trials with an IND held locally by the IU principal investigator or university, the IND Annual Report will be prepared and submitted to the Compliance Team. This report will be reviewed by the DSMC at the time of FDA submission.

12.2 Study Auditing and Monitoring

All trials conducted at the IUSCC are subject to auditing/monitoring. Reports will be forwarded to the DSMC for review.

12.3 Data Management/OnCore Reporting Requirements

The DSMC reviews data and study progress directly from Oncore; therefore, timely data entry and status updates are vital. Study data must be entered within Oncore promptly, no later than one week from study visit occurrence. Subject status in Oncore will be

updated in real time, as this may affect overall trial enrollment status. Global SAEs and deviations will be reviewed on a monthly basis by the DSMC Chair directly from Oncore.

12.4 OnCore Safety Reporting

In addition to protocol- and regulatory-required safety reporting, all serious adverse events (SAEs) will be captured in the Oncore system within 1 business day of notification. Initial SAE reporting will include as much detail as available, with follow-up to provide complete information.

Attributions will be assessed to study drugs, procedures, study disease, and other alternate etiology.

12.5 Study Accrual Oversight

Accrual data will be entered into the IU Simon Cancer Center OnCore system. The Protocol Progress Committee (PPC) reviews study accrual twice per year while the PPC coordinator reviews accrual quarterly.

12.6 Protocol Deviation Reporting

Protocol deviations will be entered into OnCore within 5 days of discovery and reviewed by the DSMC Chair on a monthly basis. Findings will be reported to the full DSMC at the time of study review. For serious or repetitive protocol deviations, additional action may be required by the DSMC.

13 ADVERSE EVENTS

13.1 Definitions of Adverse Events

13.1.1 Adverse Event

An adverse event (AE) is defined as any untoward medical occurrence associated with the use of a drug in humans, whether or not considered drug related. An adverse event can be any unfavorable and unintended sign (e.g. an abnormal laboratory finding), symptom, or disease temporarily associated with the use of a drug, without any judgment about causality. Adverse events will be graded according to the NCI Common Toxicity Criteria, Version 4.0 (Appendix A).

13.1.2 Serious Adverse Event (SAE)

A serious adverse event is any untoward medical occurrence resulting in one or more of the following:

- Results in death or ANY death occurring within 28 days of last dose of study drug (even if it is not felt to be drug related)
- Is life-threatening (defined as an event in which the patient was at risk of death at the time of the event; it does not refer to an event which hypothetically might have caused death if it were more severe)
- Requires inpatient hospitalization or prolongation of existing hospitalization

NOTE: Hospitalizations that are not considered SAEs are:

- Hospitalization planned prior to first administration of study drug
- Hospitalization for elective treatment of a pre-existing condition unrelated to the study medication
- Results in persistent or significant disability/incapacity
- Is a congenital anomaly or birth defect
- Is an important medical event (defined as a medical event(s) that may not be immediately life-threatening or result in death or hospitalization but, based upon appropriate medical and scientific judgment, may jeopardize the patient or may require intervention (e.g., medical, surgical) to prevent one of the other serious outcomes listed in the definition above). Examples of such events include, but are not limited to, intensive treatment in an emergency room or at home for allergic bronchospasm; blood dyscrasias or convulsions not resulting in hospitalization; or the development of drug dependency or drug abuse.

13.1.3 Unexpected Adverse Event

An adverse event not mentioned in the Investigator's Brochure or package insert or the specificity or severity of which is not consistent with the Investigator's brochure or package insert.

13.1.4 Determining Attribution to the Investigational Agent(s)

Attribution: An assessment of the relationship between the AE and the medical intervention. CTCAE does not define an AE as necessarily “caused by a therapeutic intervention”. After naming and grading the event, the clinical investigator must assign an attribution to the AE using the following attribution categories:

Relationship	Attribution	Description
--------------	-------------	-------------

Unrelated to investigational agent/intervention	Unrelated	The AE is clearly NOT related
	Unlikely	The AE is doubtfully related
Related to investigational agent/intervention	Possible	The AE may be related
	Probable	The AE is likely related
	Definite	The AE is clearly related

13.2 Adverse Event Reporting Requirements:

Adverse events will be recorded for the study drug administration) regardless of whether or not the event(s) are considered related to trial medications. All AEs considered related to trial medication will be followed until resolution, return to baseline, or deemed clinically insignificant, even if this occurs post-trial.

13.2.1 Reporting to the IRB:

Unanticipated problems involving risks to subjects or others will be reported **promptly** to the IRB if they:

- unexpected;
- related or possibly related to participation in the research; and
- suggest that the research places subjects or others at a greater risk of harm than was previously known or recognized.

If the serious adverse event does not meet all three (3) criteria listed above, the event does not have to be promptly reported to the IU IRB. However, it should be reported at the time of continuing review.

Prompt reporting of unanticipated problems to the IRB is defined as within 5 days from becoming aware of the event.

13.2.2 Reporting to the IUSCC Data Safety Monitoring Committee:

Regardless of study sponsorship, the study team must enter all initial and follow-up SAE, expedited, and noncompliance reports into OnCore® for review by the DSMC chair and/or coordinator. Expedited reports may include IRB Prompt Report Forms, AdEERS reports, MedWatch, and additional SAE forms as required by the sponsor. When follow-up information is received, a follow-up report should also be created in OnCore®. This DSMC reporting requirement is in addition to any other regulatory bodies to be notified (i.e. IRB, FDA, pharmaceutical company, etc.). The DSMC chair and/or coordinator will review all SAE, expedited, and noncompliance reports monthly.

14 PATIENT CONSENT AND PEER JUDGEMENT

The protocol and informed consent form for this study must be approved in writing by the appropriate IRB prior to any patient being registered on this study.

Changes to the protocol, as well as a change of principal investigator, must also be approved by the Board. Records of the Institutional Review Board review and approval of all documents pertaining to this study must be kept on file by the investigator and are subject to inspection at any time during the study. Periodic status reports must be submitted to the Institutional Review Board at least yearly, as well as notification of completion of the study and a final report within 3 months of study completion or termination.

The study will be conducted in compliance with ICH guidelines and with all applicable federal (including 21 CFR parts 56 & 50), state or local laws.

16 APPENDICES

16.1 Appendix A

NCI Common Toxicity Criteria (Version 4.0)

Due to the size of the latest version of the Common Toxicity Criteria, copies of this appendix are not included with this protocol document.

An electronic copy is available on the CTEP web site,
<http://ctep.cancer.gov/reporting/ctc.html>
